#### **C.4. Research Design and Methods**

**C.4.a: Project Overview:** The Wills Eye Glaucoma Research Center will conduct a 5-year prospective, randomized controlled trial to evaluate an innovative, community intervention using posterior fundus photographs of the optic nerve and macula to improve access and utilization of eye care to detect, treat, and manage high-risk patients with previously undiagnosed glaucoma, glaucoma suspect, and other eye diseases. L. [name]; [name]; and [name], RD, will lead the research study.

Our diverse targeted, at-risk population includes African Americans, Hispanics, and Asians over age 40; other older adults (aged 65+); individuals over age 40 with a family history of glaucoma and/or with diabetes. Approximately 1250 patients will be recruited from geographically diverse locations across Philadelphia and Chester counties, with the help of our community partners. **Phase 1** will consist of detecting eye disease in 7

primary care offices and 10 FQHC using telemedicine (Visit 1), followed by a comprehensive eye exam by a Wills glaucoma specialist in the same setting to confirm the diagnosis (Visit 2). Based on preliminary data, 30% of patients (approximately 750) will have abnormal optic nerve and/or macula images. The predictive accuracy of the optic nerve images to detect glaucoma and glaucoma suspect as confirmed by the comprehensive eye exam will be evaluated.

**Phase 2** will involve consenting, enrolling, and randomizing 374 patients to either the usual care group (n=187) or the enhanced intervention group (n=187). The enhanced intervention will consist of using patient navigators and a social worker to reduce barriers to follow-up eye care. **Phase 3** will consist of following patients proximally (6 months) and distally (3 years) while they attend appointments with a local, eye care provider (Visits 3-7). Adherence to follow-up recommendations for eye care will be the primary outcome measure. A comprehensive cost study to estimate the intervention costs and cost-effectiveness of detecting eye diseases and vision impairment in a high-risk population will also be conducted. Protocols, materials, outcomes, and results will be disseminated to other communities in order to expand detection of glaucoma, other eye diseases, and visual impairment, and to further refine these approaches to successfully scale the program up to a national level.

During the final closeout visit at the primary care office, patients will be contacted by letter (and follow-up phone call if needed) by a member of the study team and will be scheduled to return to their primary care provider for the following:

- Review of current eye medications
- Review of current systemic medications
- Review of demographics (address & phone number(s))
- Results of A1C reading (from PCP office)
- Blood pressure reading
- Intraocular Pressure reading
- Smoking status
- Completion of Satisfaction Closeout Survey
- Completion of NEIVFQ questionnaire

C.4.b. Specific Roles of Collaboration/Partnerships: The successful implementation of this research project builds upon Wills' current community partnerships from our CDC demonstration project and new collaborations and infrastructure established by the WETD. Our partnerships maximize the capacity of the intervention to reach and identify people with undiagnosed glaucoma, glaucoma suspect, other eye diseases; and visual impairment among high-risk, vulnerable patients they serve. Patients within each organization are racially and ethnically diverse, as described in Facilities. To ensure the broadest reach and ownership of the proposed intervention, our community partners have been invited to collaborate by joining the Advisory Board and engaging in planning, developing, implementing and evaluating the interventions. These partners include the Public Health Management Corporation, Philadelphia Department of Public Health, Health Federation of Philadelphia, and Temple Physicians, Inc. Since each organization has its own detection and referral system for vision and eye care services, we have developed our specific aims and study design with input from our partners and Advisory Board members (Appendix D).

Partners will also assist in remediating organizational, community, and cultural barriers and will provide facilitators and resources to ensure replication of our protocols, results, and outcomes. We believe that the breadth of the governmental, community, non-profit, and university-based partner organizations and the

diversity of the targeted at-risk patient populations will allow the results of our research to be sustainable and generalizable to other geographic areas within the United States. We will continue to work closely with each partner to refine the project goals and best methods to improve access, utilization, treatment, and follow-up eye care. The integration of these partners is essential to the proposed research structure, which will allow us to achieve a high-functioning system to overcome barriers and improve facilitators for eye disease and vision loss detection in newly diagnosed high-risk individuals (Appendix A and C).

C.4.c. Sequence of Activities: The *RE-AIM Framework* (Section D) described the aims of the proposed study and the ways our intervention is integrated into a vision and eye-care system^92. At the present time, under the leadership of [name] and [name], COA, the WETD has contracted with our partner organizations to provide fundus photography for any patient with diabetes referred by the PCP in their health system or FQHC. By partnering with our own telemedicine department, our detection and management study will be able to reach populations and individuals at high risk for vision loss and eye disease.

Beginning in January 2015, after IRB approval at all collaborating institutions, additional patients that meet our inclusion criteria will be referred and recruited as described below in Section C. Partners and Advisory Board members will contribute to the successful implementation of eye disease and functional vision loss detection interventions by providing oversight within their own organizations and health centers. They will assist with submitting IRB applications and amendments, develop satisfaction surveys for their patients, establish tracking methods to assess follow-up eye-care utilization, help determine the best methods to contact patients, and attend quarterly research meetings with Wills research staff members.

C.5.a. Case Findings/Outreach/ Recruitment: The proposed intervention has been planned and developed to detect glaucoma, other eye diseases, and functional vision loss. A significant initiative has already taken place within our partner organizations by our WETD to inform all referring PCPs about the locations where fundus photographs are taken for their patients with diabetes. Ongoing referrals have been successfully generated but only 50% of those patients scheduled show up for the detection exam. Therefore, all participants will receive reminder phone calls and letters as part of our recruitment and retention strategies.

Community partners' quality control and information technology staff have agreed to provide patient reports at each practice using the inclusion criteria. Using these lists, we will adopt "opt-out" recruitment methods so we can call all patients to describe the study, confirm eligibility, and schedule them for the detection exam (Visit 1). We will also develop customized, linguistically appropriate flyers for waiting rooms. We will submit all of these documents with our initial IRB applications at each partner institution so there are no delays in initiating recruitment. We will work with each partner's medical director to develop these materials. All eligible patients who are scheduled for Visit 1 will receive a personal phone call to remind them of the appointment, discuss the importance of attending this visit, and answer any questions. Many patients lack knowledge regarding the permanency of vision loss due to glaucoma and diabetes and even perceive that it is not important to attend all follow-up visits. Therefore, our study staff will continue to educate patients through phone calls and personal contact. A total of up to 3 attempts will be made in total to schedule or reschedule cancelled/no-show appointments.

C.5.b. Inclusion/Exclusion Criteria: The targeted, diverse, at-risk populations for the implementation research are people with previously undiagnosed glaucoma or glaucoma suspect, other eye diseases, and vision loss.

*Inclusion Criteria:*

- African-American, Hispanic, or Asian individuals over age 40
- Caucasian individuals over age 65
- Individuals of any ethnicity, over age 40 with a family history of glaucoma

- Individuals of any ethnicity, over age 40 with diabetes
- Individuals who meet one of the above criteria who have not seen an ophthalmologist in the past year

*Exclusion Criteria:* Any patient with previously diagnosed glaucoma, glaucoma suspect, or eye diseases who is currently being followed by an ophthalmologist.

C.5.c. Visit 1: Identification and Detection (PCP Office): Currently, the WETD owns and operates 2 Volk Pictor Plus auto-focus fundus cameras. Our ocular photographers, technicians and glaucoma staff have extensive experience and training using these cameras. A 3-person team comprised of 1 ocular technician and 2 study coordinators, will travel to the community sites and take posterior fundus photographs (3 per eye) using the Volk Pictor Plus camera. Monoscopic and stereoscopic optic nerve images and the macula of each eye will be visible.

The footprint for data acquisition consists of the patient, an imaging device/acquisition system, and a laptop computer. Approximately 25 patients are able to receive undilated fundus photographs of the optic nerve and macula in a 4-hour period. We will also assess the patient's medical and ocular history, family history of glaucoma, and eye pressure using rebound tonometry.

NOTE: A single IOP measurement will be obtained using the iCare tonometer for each eye. If IOP measurement is  $>22\text{mmHg}$ , a second IOP measurement will be obtained. If the difference between the 2 measurements is  $\leq 2\text{mmHg}$ , the average between the 2 measurements will be calculated and recorded. If the difference between the IOP is  $>2\text{mmHg}$ , a third measurement will be obtained and the median value of the 3 measurements will be recorded.

Standard measures of vision impairment, including visual acuity using the Snellen chart will also be conducted. Together, these results and the patient's images will be forwarded immediately to the Wills Eye Telemedicine Reading Center. Also during Visit 1, the research staff will document blood pressure, A1C, and BMI from the patient's PCP medical record. Our telemedicine infrastructure has laid the groundwork for this 5-year research project.

NOTE: During Visit 1 if the IOP is elevated based on the criteria outlined below by glaucoma specialists, the subject will be asked to skip Visit 2 and will be eligible to continue to Visit 3 with the local ophthalmologist. The subject will sign the Part II consent and get randomized during Visit 1. They will also complete the NEI-VFQ-25. If the subject chooses not to continue with the study, the team along with the PCP will make sure to stress the importance of seeing an ophthalmologist of their choosing in the time frame outlined.

IOP in either eye  $> 30\text{ mm Hg}$  subject to visit ophthalmologist within 2 weeks  
 IOP in either eye  $> 35\text{ mm Hg}$  subject to visit ophthalmologist within 1 week  
 IOP in either eye  $> 40\text{ mm Hg}$  subject to visit ophthalmologist within 1 day

A Wills Eye Hospital ophthalmologist will call a local eye care provider to advise them of the elevated eye pressure and the need for a timely appointment.

When images are received at WETD, a trained reader reviews the data and confers with the glaucoma and/or retina specialist, who determines if clinical pathology merits further evaluation and treatment and establishes relevant diagnoses. In addition to glaucomatous changes and DR, ocular hypertension, cataract, branch retinal vein and arterial occlusion, central retinal vein and arterial occlusion, epi-retinal membrane, macular degeneration, drusen and pigmentary disturbance will be documented on the report. Reports (Appendix F) are

uploaded to a secure password-protected, HIPAA-compliant web site, where the PCPs can access these records and link the report to their own patient’s medical record. Patients with ocular pathology or patients who have photographs that are unreadable will be contacted and scheduled within 1-2 months for Visit 2 to confirm the diagnosis. Any patient with emergency eye issues, such as a detached retina, will be called immediately and scheduled for Visit 2. The patient’s PCP will also be notified by phone immediately and a follow-up letter will be sent to the patient’s home.

**C.5.d. Ongoing Education/Training/Fidelity:** Extensive training will take place during Phase 1 to ensure that all research staff adhere to policies and procedures. The Director of the Department of research and Glaucoma research center will be responsible for training Wills Eye Department of Research staff in cultural competency. The Director of Operations for Wills Eye Hospital’s Telemedicine Department will be responsible for ongoing training on the Volk Pictor Plus camera for all ocular technicians and study staff. Glaucoma specialists will be trained to read the optic nerve images. Study Investigators will develop letters to send to local ophthalmologists to inform them about the study and invite them to participate. In addition, but before we begin the study, in conjunction with our general ophthalmology advisor, we will plan and develop definitions of adherence for all patients during Visits 3-8.

**C.6. Visit 2: Baseline Assessment Measures and Confirming Diagnosis (PCP Office):** Patients who have been diagnosed with glaucoma, glaucoma suspect, other eye diseases, vision impairment or have photographs that are unreadable who require non-emergent follow-up, will be notified by mail and telephoned by the study staff to schedule Visit 2 within 4 weeks of the detection visit. We will call all patients to remind them of the exam, discuss steps to prepare for an eye exam, and answer any questions. There will be no cost for this comprehensive eye exam. Any patient with an emergency eye issue at Visit 2 will be contacted immediately by phone and scheduled for an appointment at Wills Eye Hospital.

To conduct Visit 2, a leased van will transport the research team and all necessary equipment to the site each day. During the visit, an ocular technician and a glaucoma specialist will assess the patient’s ocular, systemic, and family history and conduct a undilated eye exam including: 1) visual acuity measurement using Snellen eye charts, 2) slit-lamp biomicroscopy of the anterior segment, 3) IOP, 4) undilated optic nerve head evaluation (although if patient has diabetes they may be dilated),5) central corneal thickness measurement, 6) visual field analysis using the Octopus visual field analyzer and 7) gonioscopy.

The glaucoma specialist will review the results and final diagnosis with each patient. Criteria for glaucoma or glaucoma suspect will be defined as IOP (>21mm Hg), suspicious disks including a cup-to-disk (C:D) ratio greater than 0.5, C:D asymmetry (> 0.2), disk hemorrhage, or a combination of IOP and C:D appearance. Other eye disease diagnoses, such as DR, will be made using standard *AAO Practice Pattern Guidelines*. Assessment measures and study schedule for Visits 1 through 8 are shown in Table 5.

**Table 5: Assessment Measures and Study Schedule** (PCP=Primary care physician, OPHTHO=general ophthalmologist)

Assessment Measures	Eye Detection Exam Visit 1 PCP	Confirm Diagnosis Baseline Visit 2 PCP	Initial Follow-Up Eye Exam Visit 3 OPHTHO	Ongoing Follow-Up Eye Exam Visit 4 OPHTHO	Ongoing Follow-Up Eye Exam Visit 5 OPHTHO	Ongoing Follow-Up Eye Exam Visit 6 OPHTHO	Ongoing Follow-Up Eye Exam Visit 7 OPHTHO	Final Follow-Up Visit 8 or Final Visit PCP & OPHTHO
Medical, family history	✓	✓	✓	✓	✓	✓	✓	✓
Eye fundus photographs	✓							
Complete eye exam		✓	✓	✓	✓	✓	✓	✓

Intraocular pressure**	✓	✓	✓	✓	✓	✓	✓	✓
Central Corneal Thickness*		✓	✓	✓	✓	✓	✓	✓
Visual field test*		✓	✓	✓	✓	✓	✓	✓
Visual acuity (Snellen)*****	✓	✓	✓	✓	✓	✓	✓	✓
Blood pressure (PCP) ***	✓							✓
Hemoglobin A1C (PCP) ***	✓							✓
Body mass index (PCP) ***	✓							✓
Smoking status	✓	✓	✓	✓	✓	✓	✓	✓
NEI-VFQ-25		✓			✓			✓
Satisfaction survey****	✓	✓	✓	✓	✓	✓	✓	✓
Current eye medications								✓
Current systemic meds.								✓
Confirm type of health insurance								✓
Current demographics (address & phone number(s))								✓

\* Testing will be performed at the discretion and according to the follow-up recommendation of the local ophthalmologist

\*\* IOP at Visit 1 & final visit will be measured by iCARE rebound tonometer by study team.

\*\*\* A1C will be captured from the medical record. Blood pressure will be taken at the final visit by a member of the study team.

\*\*\*\* Satisfaction surveys will be administered for Visit 1 and Visit 2 and then 2-4 times a year based on randomization; a study closeout satisfaction survey will be administered at the final visit.

\*\*\*\*\* Visual Acuity (Snellen) will be taken by study team at the final visit.

**C.6.a. National Eye Institute-Visual Function Questionnaire (NEI-VFQ):** A member of the research team will consent all patients and administer the validated NEI-VFQ-25 questionnaire at Visit 2, Visit 5 and Visit 8 to assess barriers and the influence of their vision impairment on their health-related quality-of-life. The 12 subscales are calculated by adding the relevant items and transforming the scores into a scale from 0 to 100. Higher scores indicate better quality-of-life. The composite score will be calculated as the average of 12 subscale scores. Patient navigators will use these results to assess barriers and refer patients to appropriate professionals, such as a social worker, low vision specialist, psychiatrist, occupational therapist, Medicare/Medicaid insurance advisor, and/or cataract surgeon. All materials will be culturally and linguistically appropriate and translated into other languages as necessary using trained medical interpreters and we will track all process measures.

\*NEIVFQ surveys will be administered in person to all patients at Visit 2. For Visits 5 and 8 questionnaires will be administered over the phone by a patient navigator or social worker.

**C.6.b. Patient Satisfaction Survey:** With assistance from Westat, our partners, and Advisory Board members, we will create a new survey instrument and administer it at the end of each of the study visits. We will ask patients to rate their satisfaction with the exam, its duration, its convenience, the staff, and the likelihood of attending a follow-up eye exam. These surveys will optimize patient engagement and report outcomes that are important to patients and stakeholders.

\*Satisfaction surveys will be administered in person to all patients for Visits 1 and 2. For Visit 5 surveys will be administered over the phone by a patient navigator or social worker for all enrolled patients. For Visits 3, 4, 6, and 7 satisfaction surveys will be administered according to randomization. For Visit 8 (or final visit), a Study Closeout Satisfaction Survey will be administered at the primary care office by a member of the study team.

Usual care patients will be mailed the survey with a self-addressed stamped envelope to return the instrument to Wills Eye Hospital upon completion. Intervention group patients will be called and the survey will be conducted over the phone by a patient navigator or social worker. Satisfaction surveys will be administered 2 to 4 times a year within a 4 week window of their follow-up visit.

[figure not shown]

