## **Research Question/Specific Aims**

**Aim 1)** Determine the effectiveness of an innovative, telemedicine, community-based intervention using fundus photography of the optic nerve and macula to increase the detection of previously undiagnosed glaucoma, glaucoma suspect, other eye diseases, and vision loss in high-risk populations.

*Hypothesis 1: Diagnosis of glaucoma and glaucoma suspect using undilated optic disc images, tonometry pressure results, and medical history will predict a comprehensive eye exam diagnosis.*

**Aim 2)** Evaluate the effectiveness of an evidence-based, enhanced intervention using patient navigators and a social worker to improve eye-care access, utilization, and follow-up care in community settings among those with newly diagnosed glaucoma, glaucoma suspect, other eye diseases, and vision impairment.

*Hypothesis 2: Patients randomized to the enhanced intervention group will have higher rates of adherence to follow-up eye care with general ophthalmologists over a 3-year period than the usual care group.*

**Aim 3)** Conduct a comprehensive cost study to estimate the intervention costs and cost-effectiveness of detecting eye diseases and vision impairment in a high-risk population.

*Hypothesis 3: The enhanced intervention group will be cost-effective compared to usual care and consistent with commonly cited cost-effectiveness thresholds.*

**Aim 4)** Replicate and disseminate protocols, materials, tools, and results with other communities in order to develop a public health repository of interventions to detect, manage, and follow-up patients with glaucoma, other eye diseases, and vision impairment.

*Hypothesis 4: The replication and dissemination of study materials will allow further refinement and sustainability of these interventions for national implementation in additional community settings.*

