## **E.2. Data Analysis for Aims 1 and 2**

**E.2.a. Primary Analysis for Aim 1:** The primary analysis for Aim 1 will be to estimate the positive predictive value (PPV) of the teleophthalmology intervention for diagnosing of glaucoma. We hypothesize that the diagnosis of glaucoma and glaucoma suspect using undilated optic disc images, tonometry pressure results, and medical history will predict the comprehensive eye exam diagnosis. That is, we will calculate the proportion of patients diagnosed with glaucoma or glaucoma suspect whose diagnosis was confirmed at Visit 2 with an exact two-sided binomial confidence interval. We will conclude that the telemedicine intervention has good performance if the lower bound of the confidence interval is above 80%.

The expected sample size for this aim is 250 patients as we anticipate approximately 50% of those diagnosed with eye pathology and who return for the confirmation Visit 2 will have been diagnosed with glaucoma or glaucoma suspect at Visit 1. Data from Maa (2014) can be used to estimate the PPV for glaucoma at 85%. With 250 patients, we have 50% power to conclude the PPV is greater than 80% if the true PPV is 85% and over 99% power to conclude the PPV is greater than 80% if the true PPV is 90% using a 2-sided test with alpha=0.05. We will repeat this analysis looking at the proportion of patients diagnosed with eye pathology who in fact have an ocular diagnosis (whether or not the exact abnormality was correct).

**E.2.b. Primary Outcome Measure for Aim 2:** Patient baseline demographic and clinical characteristics will be summarized overall and by randomization assignment (in Aim 2) using means, medians, standard deviations, and ranges or frequencies and percentages, as appropriate. Our general approach from the randomized trial is to analyze patients as randomized regardless of the amount of intervention received. The primary outcome measure for Aim 2 is attendance at recommended follow-up visits (Visit 4 and later). Since the expected

number of appointments will differ based on diagnosis and disease severity, which may change over time, attendance will be summarized annually.

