E.3.b. Effectiveness Measure for Aim 3: In addition to conducting a comprehensive examination of costs, we will systematically examine these costs in the context of the intervention's societal benefits by conducting a formal cost-effectiveness analysis. The cost-effectiveness analysis will employ quality-adjusted life years (QALYs) as the primary measure of societal benefits. We will capture QALY over the course of 2 years using the Health Utilities Index, v.2/3 (HUI-2/3). HUI-2/3 is a utility measurement instrument that consists of 15 items that capture 8 attributes of health-related QoL: vision, hearing, speech, ambulation, dexterity, emotion, cognition, and pain.

The scoring algorithm will be obtained from Health Utilities, Inc. and is based on Canadian health preference weights. Utility scores from this instrument range from 0-1, with a higher score indicating better quality-adjusted life. Previous research has shown that the HUI-3 has consistent validity in people with glaucoma, diabetic retinopathy, and cataracts. QALY will be measured as the amount of utility gained or lost over each year of the program.

E.3.c. Incremental Cost-Effectiveness Ratio: The primary cost-effectiveness measure will be defined as the incremental difference between cost of the enhanced intervention and usual care, divided by the difference in health utility-Incremental Cost Effective Ratio (ICER). The ICER thus will indicate the additional costs to bring about one additional unit of benefit (QALY) from the enhanced intervention compared to usual care. The

reference case, which will be defined as usual care. The ICER obtained will be compared to acceptable thresholds of \$50,000 to \$100,000-QALY. A secondary measure will be cost per diagnosis made.

E.3.d. Sensitivity Analysis for Aim 3: To account for uncertainty in our primary ICER, cost and effectiveness data will be entered into a decision analytic model. This is particularly important since the study will be powered based on the primary outcome, not the cost-effectiveness measure. Sensitivity analyses will ensure robustness of the ICER. Both univariate sensitivity analysis (whereby 1 variable is changed at a time and impact on the ICER will be examined), and probabilistic sensitivity analysis (PSA), whereby all relevant variables are simultaneously modified within reasonable ranges will be conducted. Sensitivity analyses will include those variables where we anticipate “real world” uncertainty.

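### Patients with known glaucoma who have lapsed from care are eligible, so the Aim 1 PPV, the count of diagnosed patients and cost per diagnosis could include disease that was already diagnosed

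*Combined protocol and SAP*

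**What the plan says.** Section C.5.b has a single exclusion: "Any patient with previously diagnosed glaucoma, glaucoma suspect, or eye diseases who is currently being followed by an ophthalmologist". It needs two things at once, known disease and current follow-up. The inclusion list adds a condition on recent care, "Individuals who meet one of the above criteria who have not seen an ophthalmologist in the past year", and is silent on prior diagnosis.

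The stated purpose is narrower. Aim 1 is "to increase the detection of previously undiagnosed glaucoma, glaucoma suspect, other eye diseases, and vision loss in high-risk populations". The sentence that introduces the criteria in C.5.b describes the target as "people with previously undiagnosed glaucoma or glaucoma suspect, other eye diseases, and vision loss", and Aim 2 is framed "among those with newly diagnosed glaucoma, glaucoma suspect, other eye diseases, and vision impairment".

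Three measures depend on who is counted:

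- **PPV (E.2.a, primary for Aim 1):** "we will calculate the proportion of patients diagnosed with glaucoma or glaucoma suspect whose diagnosis was confirmed at Visit 2". The hypothesis is that diagnosis "using undilated optic disc images, tonometry pressure results, and medical history will predict the comprehensive eye exam diagnosis". Good performance is declared if the lower limit of the exact two-sided confidence interval exceeds 80%.
- **Number of patients diagnosed (Table 8):** a process measure covering glaucoma, suspect and other eye disease.
- **Cost (E.3.c):** "A secondary measure will be cost per diagnosis made".

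None of them is limited to new diagnoses. Ocular history is taken at Visit 1 (C.5.c) and again at Visit 2 (C.6), but nothing in the plan uses it to define an analysis set. The sponsor's earlier project did make the split: Table 3 gives existing glaucoma its own column.

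**The concern.** A patient told of glaucoma some years ago who has not seen an ophthalmologist in the past year meets the criteria as written. If enrolled, that patient could be credited to the programme as a detection, although Aim 1 concerns people whose disease nobody had yet found.

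The PPV is the most exposed measure because it carries a pass/fail rule. Medical history is part of the Visit 1 diagnosis, and the Visit 2 specialist also takes an ocular history, so a known diagnosis could inform both the telemedicine call and its confirmation. If known cases are confirmed more often than new ones, the pooled PPV exceeds the PPV in undiagnosed patients, and the 80% rule is then applied to a population that does not match the aim. Cost per diagnosis would look lower than the cost of finding a new case.

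**Working it through.** **1. The plan's own power figure.** Inputs from E.2.a: n = 250, exact two-sided 95% interval, success if the lower limit is above 80%. The lower limit for x confirmed is the 0.025 quantile of Beta(x, n − x + 1). At x = 212 it is 0.797 and at x = 213 it is 0.802, so success needs at least 213 of 250. With X ~ Bin(250, p), P(X ≥ 213) is:

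- p = 0.80: 2.1%
- p = 0.85: 50.8% (plan: 50%)
- p = 0.90: 99.4% (plan: over 99%)

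The stated power reproduces. The question is who is counted, not the arithmetic.

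**2. How many known cases might enter.** The documents give no lapsed share for this trial. Table 3 of the earlier project gives 52 glaucoma, 276 suspect and 85 existing glaucoma. The PPV covers glaucoma or suspect, so the comparison base is 52 + 276 = 328. Assumption: 10-50% of the 85 are lapsed and enrol, which is 8.5 to 42.5 patients.

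- Added to the count: 8.5/328 = 2.6%; 42.5/328 = 13.0%.
- Fall in cost per such case at fixed total cost: 1 − 328/336.5 = 2.5%; 1 − 328/370.5 = 11.5%.
- Share f of all glaucoma-or-suspect cases: 8.5/336.5 = 2.5%; 42.5/370.5 = 11.5%.

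**3. Effect on the PPV rule.** Let the true PPV in undiagnosed patients be exactly 80%, and let known cases be confirmed with probability c = 0.95 to 1.00 (assumption). Pooled PPV = (1 − f) × 0.80 + f × c. With k = 250f known cases, rounded, the number confirmed is Bin(250 − k, 0.80) + Bin(k, c), and success is still at least 213.

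| f | k | Pooled PPV | Chance of declaring good performance |
|---|---|---|---|
| 0 | 0 | 80.0% | 2.1% |
| 2.5% | 6 | 80.4-80.5% | 2.9-3.2% |
| 11.5% | 29 | 81.7-82.3% | 8.7-12.9% |

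**4. Cost of restricting to new cases.** If the k known cases are removed and not replaced, the same exact rule gives:

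| n | Needed | Power at PPV 85% | Power at PPV 90% |
|---|---|---|---|
| 250 | 213 | 50.8% | 99.4% |
| 244 | 208 | 50.1% | 99.3% |
| 221 | 189 | 46.0% | 98.7% |

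**The case against.** **Intent.** The opening sentence of C.5.b names undiagnosed disease as the target, and staff telephone patients to confirm eligibility. That shows intent. But eligibility is confirmed against listed criteria, and none of them removes a lapsed known case.

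**Mechanism.** No section says that a reported past diagnosis makes a patient screen-positive. Section C.5.c has a reader and a specialist judge the transmitted data, and the Visit 2 criteria in C.6 rest on eye pressure and disc findings, not on prior diagnosis. This stands. A higher PPV from known cases is plausible, but the documents do not show that it would occur or how large it would be.

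**Size.** A reader might set the 8.5 to 42.5 assumed patients against the 52 definite new glaucoma cases and infer that yield rises 16-82% (8.5/52 to 42.5/52) and cost per case falls 14-45%. That base is wrong for these measures: the PPV includes suspects, and cost per diagnosis is not confined to glaucoma. A reader might also treat all 85 as lapsed, giving a share of 85/(85 + 328) = 20.6% and a success chance of 21-36%. Table 3 does not say who had lapsed, so that is a ceiling rather than an estimate. The earlier project also enrolled a different population, African Americans over 50 and other adults over 60 (C.2.a).

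**Scope.** Detection yield is not a named endpoint, and the Table 8 count is a process measure. The primary cost measure, the ICER, compares the two arms and does not depend on counting diagnoses. Both points stand.

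**Estimand.** A PPV in everyone screened is a legitimate description of the programme. That is a reason to report it, but it does not by itself answer Aim 1.

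**Conclusion.** The mismatch between eligibility, aim and analysis is in the text and does not depend on any assumption: lapsed patients with known disease can enrol, and none of the three measures sets them apart. What follows from it is a possibility. Such patients could be counted; the documents do not establish that they would be, or in what number.

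Under the assumed 10-50% lapsed share of the 85 earlier cases, the count of glaucoma-plus-suspect cases rises by about 2.6-13% and cost per such case falls by about 2.5-11.5%. With the further assumptions of a true PPV of 80% in undiagnosed patients and 95-100% confirmation of known cases, the chance of declaring good performance goes from 2.1% to about 3-13%. The upper part of that range matters for a pass/fail rule; the lower part hardly does. Because the lapsed share cannot be known in advance and the remedy is cheap, the plan should be changed.

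**What to change.** Leave eligibility as it is. Then:

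1. At Visit 1, use the ocular history to record whether the patient has ever been told of glaucoma, glaucoma suspect or another eye disease, and which.
2. Define the primary Aim 1 PPV, the count of newly detected cases and cost per diagnosis on patients without a prior diagnosis.
3. Report previously diagnosed patients separately, and give the PPV in all screened patients as a supporting result.
4. Restate the Aim 1 sample size and power for the new denominator.

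The cost is one analysis variable from data already planned and a slightly smaller denominator. Under the assumptions above, n falls from 250 to between 244 and 221, with power of about 50% to 46% at a true PPV of 85% and about 99% at 90%. The flag is only as good as the history taken, so the wording of the question should be fixed before enrolment.
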